- Have no prevalent diagnosis of Alzheimer's disease or related dementia and not previously screened for AD as part of a research study.
- Family members will be 21 years or older and identified by the patient as the person who would most likely assist with activities of daily living and/or medical decision making if the patient needed assistance.
- See Table 1 for patient and caregiver inclusion and exclusion criteria

Table 1. Inclusion and exclusion criteria for the proposed trial

Inclusion Criteria	
Patients	Family Members
65 years or older	21 years of older
At least one visit to primary care practice within past 24 months	Lives with the patient or lives within a 50 mile radius
Ability to provide informed consent	Ability to provide informed consent
Ability to communicate in English	Ability to communicate in English
	Identified by patient as the person most likely to provide them care if needed
Exclusion Criteria	
Patients	Family Members
Has a diagnosis of AD as determined by ICD-10 code	Is a non-family member who is not a legal Healthcare Power of Attorney
Evidence of a prescription for a cholinesterase inhibitors or memantine	
Has a serious mental illness such as bipolar or schizophrenia as determined by ICD-10 code	Has a serious mental illness such as bipolar or schizophrenia as determined by ICD-10 code
Permanent resident of a nursing facility	Has a diagnosis of AD as determined by ICD-10 code
Is already enrolled in HABC programs	

Recruitment Sites (as of 9/17/18):

- Indiana University Health Primary Care Practices
- Eskenazi Health Primary Care Practices

Primary outcome: Family member quality of life at 24 months.

Co-Primary outcomes: Family member depressive symptoms and family member anxiety at 24 months.

Co-Secondary outcomes: Family member caregiving preparedness and caregiving self-efficacy at 24 months.

Exploratory outcome: Comparison of all outcomes (noted above) between the family members in Screen Only vs. Screen Plus groups.

Table 2. Measures

Outcomes	Construct/Core Attributes	Outcome measure(s)	Name of Measure	Description	Scoring	When	Source
Primary outcome	Family member Quality of Life	Quality of Life	Medical Outcomes Study Short Form Health Survey 36 (SF-36)	36-items that measure health-related quality of life, mental, physical, and social functioning	Scores range 0-100; Higher scores more QOL	Baseline 6 mos. 12 mos. 18 mos. 24 mos.	Family reported Patient reported

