- **Multi-level mixed effects models** will be used to examine differences in SF-36 scores for both patients and family members using dyadic analytic approaches. For this aim, we will compare family members in the two screening groups (Screen Only and Screen Plus) to those in the no screening (Control) group. Repeated SF-36 scores from both patients and family members will be included as the outcome variables with participant type (patient or family member), group (Screening Only and Screening Plus versus Control), time, and interaction between groups and time as independent variables. We will use a multi-level variance-covariance matrix in the mixed effects models to account for two sources of potential correlations. Correlations from measures obtained from the same individual over time, an autoregressive correlation will be used. Correlations within a dyad between a patient and his/her family member. A compound symmetry structure will be used for the within-dyad correlation. Parameter estimation and hypothesis tests for the mixed-effects models will be conducted using the maximum likelihood approach that provides robust estimation under the missing at random mechanisms.
- A significant interaction between group and time would indicate differences in changes of SF-36 over time between the two screening groups compared to the no screening group. Absence of significant interactions, significant main group effects will suggest differences in SF-36 between groups' at all follow-up times. For Hypothesis 1 we will use a linear contrast for SF-36 from family members in the combined screening groups (Screen Only and Screen Plus) versus the no screening (Control) group at 24 months. We will also include additional covariates in the mixed effects models to determine whether family member characteristics (relationship to patient, frequency or types of contact, etc.) and knowledge of screening are associated with the outcome measures.

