- The multi-level mixed effects models provide a powerful modeling framework for analyzing dyadic outcomes. An alternative model using family member outcomes as the dependent variable and patient outcomes as an independent variable would underestimate variances in outcome measures by ignoring the randomness in the patients' outcomes by treating patient outcomes as fixed covariates. In our proposed models, correlations between patients and their family members on outcome measures (congruence) are explicitly included in the mixed effects models and estimated using maximum likelihood approach. The inclusion of the additional covariance structure due to repeated measures and within dyad correlation also makes it possible to estimate potential differences in patient-family member congruence over time. Comparisons on patient-family member congruence among the groups will be conducted using the likelihood ratio test (LRT) derived from a mixed effects model using group specific correlation structure versus a model using the same correlation in all groups. Changes in congruence can also be conducted using LRT comparing a mixed effects model with time specific correlation structure versus a model using equal correlations across time. By re-aligning data from the family member at specific lag time behind measures from patients, we will also be able to detect a lag effect in family member outcomes using this modeling framework.

Secondary Aim

- **Separate mixed effects models** with PHQ-9 or GAD-7 scores collected at baseline, 6, 12, 18 and 24 months from both patients and family members will be used as the outcome variables for Specific Aim 2. Participant type, randomized group (Screen Only and Screen Plus versus no screening), time and interaction between group and time will be used as independent variables, similarly to the modeling procedures described in details for Aim 1 above. Linear contrasts will be used to compare PHQ-9 and GAD-7 scores from family members in the combined screening groups versus the no screening group at 24 months. Dyad congruence in PHQ-9 and GAD-9 will be examined using LRT from the mixed effects models following the procedure described for Aim 1.

Secondary Aim

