assumption, results from the mixed effects models will remain unbiased if the variables contributing to the missing data are included as covariates in the models. We will also perform additional sensitivity analyses to examine whether the missing at random assumption using the selection model approach under an informative missing mechanism impacts our analyses.

Statistical Power

Sample Size and Power Considerations for COADS

For the models in Aims 1, 2 and 3, we assume a base correlation of 0.2 and a decay rate of 0.8 in a linear exponent autoregressive correlation structure for repeated measures and a continuous time response, we will need to have 540 dyads per group to have complete data at 24 month in order to achieve 82.6% power to detect a group by time interaction with an effect size of 0.24 SD with higher SF-36, lower PHQ-9, GAD-7, higher caregiver preparedness and self-efficacy scores at 24 months in the combined screening groups (Screen Only and Screen Plus) compared to family members in the no screening (Control) group. Our previous screening studies and studies in primary care had a 5% loss to follow-up (death or withdraw) within a 12-month period. Therefore, allowing a loss to follow-up rate of 10% over the 24 months, we plan to enroll 600 dyads per group into this study. For Aim 4, using similar assumptions on the correlation structure for repeated measures and also 10% attrition rate, we will have 83.4% power to detect a significant group and time interaction with an effect size of 0.28 SD comparing family members randomized to the screening plus group to those in the screening only group at 24 months. Power estimation was conducted using the GLM Power procedure in SAS.

Timeline

Table 3. Study Timeline	Year 1	Year 2	Year 3	Year 4	Year 5
Hire/ train staff					
Revise protocol manual and database					
IRB modification and approval					
Subject recruitment and consent					
Data collection					
Data analysis					
Prepare abstracts and manuscripts					
Disseminate results

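### Reading a group main effect as a difference at every follow-up time, once the group-by-time interaction is non-significant, is an unsound inference and should be removed

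*Combined protocol and SAP*

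**What the plan says.** The Primary Aim section of the Statistical Plan describes three tests on the SF-36 model.

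- Interaction: "A significant interaction between group and time would indicate differences in changes of SF-36 over time" between the screening groups and control.
- Fallback: "Absence of significant interactions, significant main group effects will suggest differences in SF-36 between" groups "at all follow-up times".
- Hypothesis test: "For Hypothesis 1 we will use a linear contrast for SF-36 from family members in the combined screening groups" versus control, at 24 months.

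No alpha is stated, and no order or hierarchy among the three is given.

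On the visits modelled, the Aim 1 text says only that "Repeated SF-36 scores from both patients and family members will be included as the outcome variables". Table 2 gives the SF-36 schedule as "Baseline 6 mos. 12 mos. 18 mos. 24 mos". The Aim 2 text is explicit that the modelled outcomes are "PHQ-9 or GAD-7 scores collected at baseline, 6, 12, 18 and 24 months". The Aim 3 and Aim 4 texts list the same five visits, and Aim 4 includes SF-36. Aims 2 and 4 say that they follow the Aim 1 approach. No baseline covariate and no common baseline mean across groups is described.

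The Statistical Power section sizes the trial on the interaction, not on the 24-month contrast: "82.6% power to detect a group by time interaction with an effect size of 0.24 SD".

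**The concern.** The fallback has three faults.

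1. Failing to reject the interaction is treated as evidence that the effect is the same at every visit. It may only reflect limited power.
2. A main effect averages over visits. It can be significant when some visits have no effect, so it cannot carry a statement about all of them.
3. Baseline is among the visits, and randomisation makes the expected group difference there zero. An effect that appears by 6 months and then stays constant is a group-by-time interaction in this model. A main effect without interaction is therefore not the pattern that such an effect produces, and the main effect is pulled towards zero by the baseline visit and shifted by any chance imbalance there.

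At stake is a published statement that screening changed family members' quality of life throughout follow-up when the data show less than that. A second, separate issue is that the plan leaves open whether the interaction or the main effect may also be used to support a hypothesis.

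**Working it through.** **Inputs.** From Statistical Power: 540 completers per group, so 1,080 versus 540 for combined screening against control; base correlation 0.2 and decay 0.8 (linear exponent autoregressive); 0.24 SD at 24 months (0.28 SD for Aim 4). From Table 2: five visits. Assumed: two-sided alpha 0.05 per test.

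Correlation at lag k is 0.2^(1 + 0.8(k − 1)/3), which gives 0.200, 0.130, 0.085 and 0.055. The effective sample size is 1,080 × 540/1,620 = 360, so the visit differences have covariance R/360, where R is the correlation matrix.

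**The plan's own figure.** A 4-df multivariate interaction test over five visits, with the difference growing linearly from 0 to 0.24 SD, has noncentrality 12.71 and power 82.61% (stated 82.6%). Aim 4 (540 versus 540, 0.28 SD) gives 83.42% (stated 83.4%). At alpha 0.025 or 0.10 the Aim 1 power would be 74.6% or 89.5%, so 0.05 is the supported assumption. A four-visit model with growth from 0 to 0.24 SD gives 82.8%, so the match favours five visits including baseline without proving it alone.

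**Dilution.** For a constant 0.24 SD after baseline, the equal-weight main effect is (0 + 4 × 0.24)/5 = 0.192 SD, and 0.192/0.24 = 0.80. The 4-df interaction is significant in 95% of such trials, so the fallback is reached in only 5% (17% with a 1-df slope test).

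**Effect of 0.15 SD at 6 and 12 months only.**

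- Main effect: (0.15 + 0.15)/5 = 0.06 SD. The entries of R sum to 7.83, so SE = √(7.83/25/360) = 0.0295, z = 2.03 and power is 53.0%.
- 1-df slope contrast (weights −2 to 2): −0.15 with SE 0.168, z = −0.89, power 14.4%. This contrast is uncorrelated with the average, so the fallback fires in 0.530 × (1 − 0.144) = 45%. A generalised-least-squares main effect gives 40%.
- 4-df interaction: noncentrality 11.4, power 77.8%. By simulation (1,000,000 draws) the fallback fires in 11%.

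In each case the true differences at 18 and 24 months are zero.

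**Planned alternative (linear to 0.24 SD, 4-df test).** The fallback fires in 17% of trials. In 24% of those, all four follow-up visits are individually significant.

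**False-positive rates under no effect, 5% per test.**

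| Route to a claim | Rate |
|---|---|
| 24-month contrast alone | 5.0% |
| Interaction, then main effect | 1 − 0.95² = 9.75% (simulated 9.7 to 9.8%) |
| Same, baseline removed from the model | 9.7 to 9.8% |
| Any of interaction, main effect or 24-month contrast | about 12.6% (11.6 to 12.8% across the correlation structures tried) |

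**Power of the contrast alone.** 0.24 × √360 = 4.55, and Φ(4.55 − 1.96) = 99.5%.

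**The case against.** The strongest reply is that the plan already names the 24-month contrast for every aim, and that all hypotheses and named outcomes are set at 24 months. That contrast holds 5%. The verbs attached to the interaction and main effect are interpretive, and nothing says that either one confirms a hypothesis. This stands. A reader might infer that the trial's false-positive rate is nearly doubled. The documents do not support that, because it needs a decision rule they do not state. What remains is that they do not exclude it, and they size the trial on the interaction.

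A reader might also infer that modelling baseline causes the inflation. It does not: the rate is the same with baseline removed, because it comes from testing twice. Baseline causes the dilution and the misreading.

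Nor is the fallback statement false under the planned linear alternative. The true differences there are 0.06, 0.12, 0.18 and 0.24 SD, all non-zero. It is unproven in that case; the early-only scenario is where it is actually wrong.

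Three limits also stand. Baseline as an Aim 1 outcome is inferred from Table 2 and the other aims. The fallback sentence appears once, so its carry-over to Aims 2 and 4 rests on their cross-reference to Aim 1, and Aim 3 has no such reference. The simulated figures depend on how time is coded, and they use complete data, a known covariance and family-member outcomes only, whereas the Aim 1 model pools patients and family members.

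**Conclusion.** Wrong as written, but it does not undermine the named test for any hypothesis, so it should be corrected without ranking as a must-fix.

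The logical fault does not depend on any simulation: neither a non-significant interaction nor a visit average can establish a difference at each visit. Its size does depend on assumptions. The dilution is 20% with equal visit weights, if baseline is modelled in Aim 1 as it is in Aims 2 to 4. For an early effect of 0.15 SD that disappears, the unsupported statement arises in about 11% of trials with categorical time and 45% with a slope test, under the planning correlations.

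The 9.7% and 12.6% are conditional. They apply only if the interaction or main effect may support a claim, and at an assumed 5% per test.

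**What to change.** In the Primary Aim section, and wherever Aims 2 and 4 take it over by reference:

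- Delete the step from a non-significant interaction to a main effect at every follow-up time.
- State that the 24-month family-member contrast alone decides each hypothesis, and give its alpha.
- Label the interaction test as descriptive.
- Report the 6-, 12- and 18-month differences as estimates with 95% confidence intervals.
- If an overall effect is wanted, define it as one supportive contrast averaging the four post-baseline visits only.

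Removing baseline from the model while keeping the two-step rule would not be enough, since the two tests would remain.

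The cost is SAP wording, with no extra data or staff. One supportive route to a positive statement is lost. The 24-month contrast keeps about 99.5% power at 0.24 SD under the planning assumptions.

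### As listed, the joint patient-family models for SF-36, PHQ-9 and GAD-7 have no participant type by group terms, so the 24-month family-member contrasts for Hypotheses 1 and 2 would estimate a patient-family average.

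*Combined protocol and SAP*

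**What the plan says.** Under Methods the target is a family-member outcome: "Primary outcome: Family member quality of life at 24 months". Hypotheses 1 and 2 likewise compare family members in the screening groups with family members in the Control group.

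The Primary Aim section of the Statistical Plan puts repeated SF-36 scores from patients and family members into one mixed model. Its listed terms are "participant type (patient or family member), group (Screening Only and Screening Plus versus Control), time, and interaction between groups and time as independent variables". On the covariance it says "A compound symmetry structure will be used for the within-dyad correlation", with an autoregressive structure within each person over time. The test is then described this way: "For Hypothesis 1 we will use a linear contrast for SF-36 from family members in the combined screening groups", against Control at 24 months.

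The Secondary Aim paragraph for Aim 2 follows the same pattern. PHQ-9 and GAD-7 scores are those "collected at baseline, 6, 12, 18 and 24 months from both patients and family members", and the terms are "Participant type, randomized group (Screen Only and Screen Plus versus no screening), time and interaction between group and time will be used". The test, again placed at month 24, reads: "Linear contrasts will be used to compare PHQ-9 and GAD-7 scores from family members in the combined screening groups versus the no screening group".

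Neither section lists participant type by group, or participant type by group by time. The Aim 3 paragraph mentions interactions with patient or family characteristics, but its model is not described as containing patient scores. The Aim 4 models use family-member scores only.

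The Statistical Power section says "we will need to have 540 dyads per group to have complete data at 24 month in order to achieve 82.6% power" for a group by time interaction of 0.24 SD in family members.

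**The concern.** When participant type enters only as a main effect, it shifts the patient and family mean curves apart by a constant. It does not allow screening to act differently on the two. The screening-versus-Control difference at 24 months is then one parameter, whether it is labelled as coming from patients or from family members. The within-dyad covariance affects weights and standard errors, but it cannot separate two effects that the mean model sets equal.

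The trial has reason to expect different responses. The patient is tested and told the result; the family member faces a possible caregiving role. The plan itself looks at patient-family congruence and at lagged family effects. If the responses differ, the listed model can dilute a real family effect or credit family members with an effect that occurred only in patients. This reaches the primary outcome.

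**Working it through.** **Inputs from the documents.** 540 completing dyads per group, so 1,080 (combined screening) against 540 (Control); five visits; repeated-measures correlation with base 0.2 and decay 0.8; effect 0.24 SD at 24 months (0.28 SD for Aim 4).

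**Assumptions.** Two-sided 5% level; effects rising linearly from zero at baseline; complete data; patient effects; within-dyad correlation r from 0.1 to 0.5; one common variance unless stated. The documents give no figure for the patient effect, for r or for the significance level. Signs follow PHQ-9 and GAD-7 (lower is better); SF-36 is the mirror image.

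**1. The plan's own power.** Take the correlation at a lag of d visits as 0.2^(1 + 0.8(d−1)/3), one respondent per dyad, and the 4-df group by time test.
- Aims 1 to 3, 0.24 SD, 1,080 vs 540: noncentrality 12.705, power 82.6%. This matches the stated figure.
- Aim 4, 0.28 SD, 540 vs 540: power 83.4%. This matches too.

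Both figures are reached with a single outcome series per dyad. The sample size therefore describes a family-only comparison, not the stacked model as listed.

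**2. What the listed model estimates.** Write f and p for the family and patient effects at 24 months. With equal variances and complete data, the contrast is (f + p)/2.
- f = −0.24, p = 0: −0.12
- f = −0.24, p = −0.24: −0.24 (no bias)
- f = 0, p = −0.15: −0.075

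**3. Standard errors.**
- Family-specific contrast: sqrt(1/1080 + 1/540) = 0.0527; 95% half-width 1.96 × 0.0527 = 0.103.
- Pooled contrast in the listed model: 0.0527 × sqrt((1 + r)/2), which is 0.0391 at r = 0.1 and 0.0456 at r = 0.5; half-widths 0.077 and 0.089.

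**4. The 24-month contrast, which is the test named for Hypotheses 1 and 2.**
- Family-specific, f = −0.24: 0.24/0.0527 = 4.55, power 99.5%.
- Listed model, f = −0.24, p = 0: 0.12/0.0391 = 3.07 and 0.12/0.0456 = 2.63, power 87% and 75%.
- Listed model, f = 0, p = −0.15: 0.075/0.0391 = 1.92 and 0.075/0.0456 = 1.64, rejection in 48% and 38% of trials. The rate should be 5%, because family members do not change.

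**5. The 4-df group by time test, on which the sample size rests.** The noncentrality becomes 12.705 × (contrast/0.24)² / ((1 + r)/2).
- f = −0.24, p = 0: 12.705 × 0.25/0.55 = 5.78 and 12.705 × 0.25/0.75 = 4.24; power 45% and 34%, against 82.6%.
- f = 0, p = −0.15: 12.705 × 0.0977/0.55 = 2.26 and 12.705 × 0.0977/0.75 = 1.65; rejection 19% and 15%.

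| Scenario | Quantity | Listed model (r = 0.5 to 0.1) | With interactions |
|---|---|---|---|
| Family −0.24, patient 0 | 24-month estimate | −0.12 | −0.24 |
| | power, 24-month contrast | 75% to 87% | 99.5% |
| | power, 4-df test | 34% to 45% | 82.6% |
| Family 0, patient −0.15 | 24-month estimate | −0.075 | 0 |
| | rejection, 24-month contrast | 38% to 48% | 5% |
| | rejection, 4-df test | 15% to 19% | 5% |

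**6. Unequal variances.** If the fitted covariance lets the variances differ and the patient SD is 1.5 times the family SD, the family weight is (2.25 − 1.5r)/(3.25 − 3r). That is 0.69 at r = 0 and 0.80 at r = 0.4, so a family effect of −0.24 SD with no patient effect is estimated as about −0.17 to −0.19 SD. A smaller patient SD would shift the weight the other way.

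**The case against.** The strongest reply is that the plan names its target repeatedly. The hypotheses, the primary outcome, the contrasts and the power statement all refer to family members, and the Primary Aim section describes its approach as dyadic. Under a purely additive type term, a contrast specific to family members would mean nothing, so the list may simply be abbreviated. This is a fair reading, and it makes the point a specification omission rather than a known bias. It does not settle the matter. An analyst who follows the term list gets the pooled estimate; one who follows the contrast wording must add unlisted terms, and that choice would be made after the data exist.

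A second reply is that the harm depends on unequal effects, and the documents give no patient effect. That stands. With equal effects the listed model is unbiased and more precise.

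Three stronger readings are tempting, and the documents do not support them.
- A reader might infer that power for Hypothesis 1 drops from 82.6% to 34% to 45%. Those figures belong to the 4-df group by time test. Hypotheses 1 and 2 are assigned to the 24-month contrast, which keeps 75% to 87% in the same scenario.
- A reader might infer that the stated sample size is wrong. It reproduces exactly for one respondent per dyad.
- A reader might infer that the lack of a planned screening-versus-Control contrast for patient PHQ-9 and GAD-7 is a defect. No hypothesis or named outcome concerns patient mood, and the family results are sound without it.

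**Conclusion.** The point holds for the models as listed. The 24-month contrast in the SF-36, PHQ-9 and GAD-7 joint models is a precision-weighted average of the patient and family effects, exactly half and half with equal variances and complete data. It equals the stated family-member target only when the two effects are equal. That follows from the term list and needs no assumption about effect size.

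The practical size is conditional on the assumed patient effects and within-dyad correlations. A patient effect of zero halves the design effect of 0.24 SD. An improvement of 0.15 SD in patients alone raises the false-positive rate of the family contrast from 5% to between 38% and 48%. If the interactions were intended, what remains is to write them in; the plan should still be changed, because the primary analysis is affected.

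**What to change.** In the SF-36, PHQ-9 and GAD-7 joint models, add participant type by time, participant type by group, and participant type by group by time. Define the Hypothesis 1 and 2 contrasts as the family-member difference, combined screening minus Control, at 24 months. State that these estimates are family-specific and not pooled over the dyad. If this was always intended, the change is one of wording.

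The cost is a short SAP edit and three interaction terms in each of three models, on data already planned. The 82.6% power then applies to the family-specific group by time test, because it was computed with one respondent per dyad. The downside is precision: if patient and family effects are equal, the 24-month interval is 15% to 35% wider than the pooled one (half-width 0.103 against 0.089 to 0.077 SD). The same models could also report patient PHQ-9 and GAD-7 contrasts descriptively, but that is optional.

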- **Mixed effects models with Caregiver Preparedness Scale or the Revised Scale for Caregiver Self-Efficacy scores** collected at baseline, 6, 12, 18 and 24 months will be used as the outcome variables, group (Screen Only and Screen Plus versus Control), time and interaction between group and time as independent variables. Linear contrasts will be used to compare preparedness and caregiver self-efficacy scores in the combined screening groups versus the no screening group at 24 months. We will also evaluate potential interactions between patient's/family member characteristics and variables associated with increased level of caregiver preparedness and self-efficacy over time.

Secondary Aim

- **To measure the impact and compare strategies for evaluation and treatment post screening, we will compare quality of life measures, caregiver preparedness, caregiving self-efficacy, depression and anxiety symptoms from family members** in the Screen Only (notify dyad and PCP of results only) group to the Screen Plus (notify dyad and PCP and a referral to ABC Program if screen positive) group using multi-level mixed effects models, similarly to the approach described in details for Aim 1. Separate mixed effects models with SF-36, Caregiver Preparedness Scale, Revised Scale for Caregiver Self-Efficacy, PHQ-9 or GAD-7 scores collected at baseline, 6, 12, 18, and 24 months from family members will be used as the outcome variables. Screening group (Screening Only versus Screening Plus), time and interaction between group and time will be used as independent variables. Linear contrasts will be used to compare all scale scores between the two screening groups at 24 months.

Sensitivity analyses for the impact of refusals and other sources of missing data

- We will compare patient and family member characteristics between those who complete at least one or more follow-up assessment(s) after baseline and those who did not complete any assessment beyond baseline due to refusal or other reasons. Significant variables detected from these comparisons will be included in the mixed effects models for the primary and secondary outcomes as covariates to control for potential bias from those missing follow-up outcomes. Under the missing at random

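### The screen for predictors of missing data compares dyads with no follow-up against dyads with any, although every hypothesis is tested at 24 months, so it rests on about a quarter of the dyads expected to lack that outcome

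*Combined protocol and SAP*

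**What the plan says.** The section on sensitivity analyses for refusals and other missing data sets up one comparison of patient and family member characteristics. One side is "those who complete at least one or more follow-up assessment(s) after baseline"; the other is "those who did not complete any assessment beyond baseline due to refusal or other reasons". The result feeds the main analyses: "Significant variables detected from these comparisons will be included in the mixed effects models for the primary and secondary outcomes as covariates". The section then states the condition on which it relies, under missing at random (MAR): "results from the mixed effects models will remain unbiased if the variables contributing to the missing data are included as covariates in the models". A further sensitivity analysis is planned "using the selection model approach under an informative missing mechanism".

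The Primary Aim and Secondary Aim paragraphs of the Statistical Plan test each hypothesis by a linear contrast at 24 months. Visits take place at 6, 12, 18 and 24 months. The sample size section notes that earlier studies "had a 5% loss to follow-up (death or withdraw) within a 12-month period" and sets enrolment by "allowing a loss to follow-up rate of 10% over the 24 months". The plan describes no comparison by 24-month status, by last visit attended or by time of dropout.

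**The concern.** The comparison is the only stated means of finding the variables that contribute to missing data, and the plan makes its claim of unbiasedness depend on including them. Yet its dividing line is the first follow-up visit, not the visit at which the hypotheses are tested. A dyad that attends at 6 months and then withdraws lacks the 24-month outcome but is counted with those who have it.

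Two things follow. The group meant to represent missing data is small, so the screen has little power. And a baseline variable that predicts mainly later dropout gives almost no signal in it. If such a variable is also prognostic and is not otherwise in the model, the 24-month contrast loses the protection that the plan says it has.

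**Working it through.** **Inputs from the documents.** 1,800 dyads with completed baselines, 600 per arm; 540 per arm with complete 24-month data; loss of 5% per 12 months and 10% over 24; visits every 6 months.

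**Assumptions, not in the documents.** Even loss within each year; monotone dropout; the dyad as the unit; two-sided 5% level; normal approximation for the comparison of a continuous baseline variable.

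**1. The plan's own figure.** 540 / (1 − 0.10) = 600 per arm, as stated. The 10% rate is the one behind the sample size.

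**2. Where the missing dyads fall.** Even loss is 2.5% per 6 months.

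| By month | Cumulative loss | Dyads of 1,800 |
|---|---|---|
| 6 | 2.5% | 45 |
| 12 | 5.0% | 90 |
| 18 | 7.5% | 135 |
| 24 | 10.0% | 180 |

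No follow-up: 45. Missing at 24 months but with some follow-up: 180 − 45 = 135, and 135/180 = 75%. A constant hazard gives 1 − 0.95^0.5 = 2.53% at 6 months and 1 − 0.95² = 9.75% at 24 months, hence 1 − 2.53/9.75 = 74%.

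**3. Range for timing.** Keep 5% by month 12 and 10% by month 24. If all first-year loss precedes the 6-month visit, 90 of 180 have no follow-up and the share is 50%. If none does, it is 100%. Isolated misses at 24 months would raise it.

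**4. Difference detectable with 80% power.** (1.960 + 0.842) × √(1/n₁ + 1/n₂), in SD units.

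- As written, 45 vs 1,755: 2.802 × 0.1510 = 0.42 SD.
- By 24-month status, 180 vs 1,620: 2.802 × 0.0786 = 0.22 SD.
- As written with the most front-loaded timing, 90 vs 1,710: 2.802 × 0.1081 = 0.30 SD.

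**5. Which predictors each comparison can see.** Take a baseline difference of 0.3 SD, chosen for illustration, between the dropouts concerned and everyone else.

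- *Shared by early and late dropouts.* As written, the 135 late dropouts are 135/1,755 = 7.7% of the reference group, so the contrast is 0.3 × (1 − 0.077) = 0.28 SD. Dilution is slight; the low power comes from having only 45 dyads on one side.
- *Late dropouts only.* As written, the contrast is 0.3 × 135/1,755 = 0.02 SD in size, with the sign reversed, which is effectively invisible. By 24-month status it is 0.3 × 135/180 = 0.225 SD, just above the 0.22 SD detectable with 80% power.
- *Early dropouts only.* By 24-month status the contrast falls to 0.3 × 45/180 = 0.075 SD, well below 0.22 SD. A binary split at 24 months alone would lose these predictors, so the no-follow-up stratum should be kept.

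**The case against.** The strongest reply is that late dropouts need this step least. The Primary Aim paragraph commits to maximum likelihood on all repeated scores. A dyad that leaves after 6, 12 or 18 months keeps its observed scores in the likelihood, and dropout that depends on those scores or on arm is ignorable under MAR without any added covariate. Dyads with no follow-up are those about whom the model knows least, so singling them out has some logic. The plan also adds family member characteristics and knowledge of screening to the models, and it has a selection model in reserve. This stands, and it narrows the exposure to prognostic baseline variables left out of the model.

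It does not remove the point. Observed scores protect only as far as they predict the missing one. Under the correlations assumed for power (base 0.2, decay 0.8, five equally spaced visits), earlier scores explain 0.9% of the variance of a 24-month score for a dyad last seen at 6 months, 2.1% at 12 months and 5.1% at 18 months. Actual correlations may be higher. The selection model examines departures from MAR; it does not change which covariates enter the primary models.

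A reader might go further and infer that the screen cannot find predictors of later dropout, that it examines the wrong people, or that the 24-month result is biased. The documents do not support this. Predictors shared by early and late dropout can still be found, with less power. Nor is any bias shown. For illustration, suppose that late dropouts (7.5% of an arm) differ by 0.3 SD on an omitted variable correlated 0.3 with the outcome. The arm mean then shifts by 0.075 × 0.3 × 0.3 = 0.007 SD; at a correlation of 1 the shift is 0.0225 SD. If the pattern is the same in all arms the contrast does not move. If it is confined to one comparison group, these shifts are about 3% to 9% of the 0.24 SD design effect.

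The pilot's loss of under 1%, cited with the enrolment procedures, would make every count smaller, but it is not the rate used for planning.

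**Conclusion.** The point holds as a defect in how covariates are selected, not as a fault that invalidates the primary analysis. On the plan's loss rates, about 75% of the dyads missing the 24-month outcome sit in the any-follow-up group. That figure needs even, monotone loss; the yearly rates alone allow 50% to 100%, because the documents do not say when within a year loss occurs. Even at 50%, the screen reaches 80% power only for differences of about 0.30 SD or more.

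The consequence is a weak screen that may miss baseline variables mainly related to later dropout, while the plan makes unbiasedness depend on such variables being included. Whether this would move the 24-month contrast cannot be determined from the documents. The change is worth making because it is cheap and affects which covariates enter the primary and secondary models.

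**What to change.** In the section on sensitivity analyses for missing data, define the comparison by whether the family member's 24-month outcome is observed or missing. Within the missing group, keep dyads with no follow-up as the earliest stratum, so that predictors of immediate loss remain visible. Tabulate time of dropout (before 6, 12, 18 or 24 months) by arm, and say how isolated missed visits are classified.

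The cost is a changed definition and one more table, from data already collected. With 180 rather than 45 dyads in the missing group, the significance rule may admit a few more covariates to the models, some perhaps not prognostic; with about 1,800 dyads that is a minor cost.
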